The model will include the fixed categorical effects of treatment group (GZ/SAR402671 versus placebo), randomization strata (use of levodopa/PD medication: yes/no, MoCA score <26: yes/no and severe GBA mutation: yes/no), time point (as defined in Table 6), treatment-by-time point interaction, randomization strata-by-time point interaction as well as the continuous fixed covariates of baseline MDS-UPDRS Part II+III score and the baseline-by-time point interaction.

This model will be run using SAS Mixed procedure with an unstructured correlation matrix to model the within-patient errors. Parameters will be estimated using restricted maximum likelihood method. Denominator degrees of freedom will be estimated using Kenward-Roger approximation. This model will provide baseline adjusted least-squares means estimates at Week 52 for both treatment groups with their corresponding standard errors (SEs) and 95% confidence intervals (CI). The difference in baseline adjusted least-squares means will be used to compare the GZ/SAR402671 group to the placebo group, at the 2-sided 0.05 level.

Within group least-squares means and standard errors will be calculated using weights equal to the observed proportion of patients in strata variable levels in the study population (i.e. “population weight”) rather than equal weights. Population weights are considered more appropriate than equal coefficients due to expected unbalances in the study population between levels of the randomization stratification factors.

In addition, the relative reduction versus placebo will be calculated as:

$$\text{Relative reduction (\%)} = \left(1 - \frac{\text{LS mean change at Week 52 in GZ/SAR402671 arm}}{\text{LS mean change at Week 52 in placebo arm}} \right) \times 100$$

Relative reduction will be presented with 95% confidence interval using Fieller method. This confidence interval will be calculated provided a significant change is observed in the placebo arm at the 0.05 level. In addition, the posterior probability that GZ/SAR402671 achieves a relative reduction by at least 25% and 50% will be calculated using samples from the asymptotic distribution of LS means from the two treatment arms.

Sensitivity analysis including data collected after treatment discontinuation

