- Excluding any MDS-UPDRS assessed less than 6 hours after intake of PD medication (irrespective of clinical state)
- Excluding any MDS-UPDRS assessed less than 12 hours after intake of PD medication and for which the clinical state was recorded as “ON”.
- Excluding any MDS-UPDRS assessed less than 6 hours after intake of PD medication and for which the clinical state was recorded as “ON”.

The MMRM model described as primary analysis will be repeated after exclusion of these data.

Sensitivity analyses assessing randomization strata

A sensitivity analysis will estimate the difference in mean change from baseline to Week 52 in MDS-UPDRS Part II+III score after including the actual strata derived from data instead of the strata recorded in IVRS (use of levodopa/PD medication: yes/no, MoCA score <26: yes/no and severe GBA mutation: yes/no). The purpose of this analysis will be to assess the impact of discrepancies observed between the strata recorded in the IVRS and the ones derived from data. The MMRM model described as primary analysis will be repeated after including the actual strata.

Secondary analysis

A secondary analysis will describe the number and percentage of patients with MDS-UPDRS Part II+III score improvement, no change or worsening at Week 52 based on minimal clinically important difference threshold values in patients with Hoehn&Yahr 1&2 (5):

- Improvement will be defined as change in MDS-UPDRS Part II+III ≤ -4.3
- Worsening will be defined as change in MDS-UPDRS Part II+III ≥ 3.9
- No change will be defined as change in MDS-UPDRS Part II+III > -4.3 and < 3.9

Patients without any available assessment at Week 52 will be considered as worsened.

Subgroup analyses

The MMRM model described as primary analysis will be repeated in each of the following subgroups as appropriate, the p-values will not be adjusted for multiplicity and will be provided for descriptive purpose only, and forest plots will be provided:

- Sex (Male vs. Female);
- Age (≤ 60 vs. > 60);
- GBA mutations (severe vs. non severe) : Severe GBA mutation subgroup will be defined using actual subgroup (not randomization stratum as per IVRS);

- Prior PD medications (yes vs. no): Prior PD medication subgroup will be defined using actual subgroup (not randomization stratum as per IVRS);
- Time since onset of symptoms (≤ 6 years vs > 6 years);
- Time since diagnosis (≤ 6 years vs > 6 years);
- MDS-UPDRS Part II+III at baseline (≤ 35 vs. > 35);

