- Hoehn and Yahr at baseline (< 2 vs. ≥ 2);
- MoCA score at baseline (< 26 vs. ≥ 26): MoCA score subgroup will be defined using actual subgroup (not randomization stratum as per IVRS);

Unless otherwise specified (see below), for each subgroup analysis, the MMRM model will include the fixed categorical effects of treatment group, randomization strata as per IVRS, subgroup factor, time point, treatment-by-time point interaction, strata-by-time point interaction, subgroup factor-by-time point interaction, treatment-by-subgroup factor interaction, and treatment-by-subgroup-by-time point interaction, as well as the continuous fixed covariates of baseline value and baseline value-by-time point interaction. Exceptions will be made for the following subgroup analyses:

- For subgroup analyses by GBA mutation, the MMRM will not include the randomization stratum of severe GBA mutation (yes/no)
- For subgroup analyses by prior PD medication, the MMRM will not include the randomization stratum of use of levodopa/PD medication (yes/no)
- For subgroup analysis by MoCA score at baseline, the MMRM will not include the randomization stratum of MoCA score < 26 (yes/no)
- For subgroup analysis by MDS-UPDRS Part II+III at baseline (≤ 35 vs. > 35), the MMRM will not include adjustment for baseline

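### The subgroup model for baseline MDS-UPDRS Part II+III (≤35 vs >35) drops the continuous baseline score, at a small and avoidable cost in precision

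*SAP*

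**What the plan says.** SAP section 2.4.4.1 defines the primary MMRM with "continuous fixed covariates of baseline MDS-UPDRS Part II+III score and the baseline-by-time point interaction". Under its Subgroup analyses heading it states: "The MMRM model described as primary analysis will be repeated in each of the following subgroups as appropriate". The default subgroup model again carries the baseline terms: "as well as the continuous fixed covariates of baseline value and baseline value-by-time point interaction".

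Four exceptions follow. Three of them (GBA mutation, prior PD medication, MoCA) each remove the binary randomization stratum that matches the subgroup factor, and leave continuous baseline in the model. The fourth concerns the split of baseline MDS-UPDRS Part II+III at 35 points, where "the MMRM will not include adjustment for baseline". No reason is given. Subgroup p-values carry no multiplicity adjustment; they "will be provided for descriptive purpose only, and forest plots will be provided".

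Section 2.4.4.2 handles a similar case differently. Change in H&Y stage is a secondary endpoint and baseline H&Y (<2 vs ≥2) is one of its subgroups. The baseline value stays in that model and no exception is listed.

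**The concern.** Dropping a binary stratum makes sense when the subgroup factor is the actual value of the same binary variable, since the two nearly coincide. A split at 35 points is different. It is a coarse version of a continuous score, and patients within either half still differ in baseline. If baseline predicts change within the halves, removing the score leaves explainable variation in the error term, and any chance difference in baseline between arms within a half passes into that half's estimate.

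At stake is the precision of two descriptive estimates and their comparability with the rest of the forest plot, where every other row is adjusted for continuous baseline.

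**Working it through.** **Inputs from SAP section 1.3.2.** SD of change 10.01, target difference 4.06, two-sided alpha 0.05, power at least 80%, about 10% unevaluable, 108 per arm.

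**Assumed, because the SAP does not give them.** The correlation r between baseline and change, the share of patients above 35, and a normally distributed baseline.

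**Step 1: the plan's own figure.** A two-sample t-test with effect size 4.06/10.01 needs 97 per arm, and 97/0.90 rounds up to 108. The sample size reproduces and this point does not touch it. With 97 evaluable per arm, a 50/50 split leaves about 48 per arm in each subgroup.

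**Step 2: how much of baseline the cut retains.** With a proportion p below the cut, c = Φ⁻¹(p) and φ the normal density, the cut keeps k = φ(c)²/[p(1−p)] of the baseline variance. This gives k = 2/π = 0.637 at 50/50, 0.576 at 30/70 and 0.490 at 20/80. At 50/50 the correlation between cut and score is √0.637 ≈ 0.80. The corresponding variance inflation factor is 1/(1−0.637) ≈ 2.75, so both terms can be fitted together.

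**Step 3: precision lost at Week 52.** As a share of the total variance of change, the residual variance is 1 − r² with the continuous score and 1 − k·r² with the cut alone. The standard errors are therefore in the ratio √[(1 − k·r²)/(1 − r²)]. The 95% CI half-width is 1.96 × 10.01 × √(residual share × 2/48).

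| r | SE increase, 50/50 | SE increase, 20/80 | Half-width without / with score (50/50) |
|---|---|---|---|
| 0.2 | 0.8% | 1.1% | 3.95 / 3.92 |
| 0.3 | 1.8% | 2.5% | 3.89 / 3.82 |
| 0.4 | 3.4% | 4.7% | 3.80 / 3.67 |
| 0.5 | 5.9% | 8.2% | 3.67 / 3.47 |

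At 50/50 the share of residual variance removed by keeping the score is 1.5%, 3.5%, 6.5% and 10.8% in the same order.

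**Step 4: chance imbalance is the same loss in other units.** Take r = 0.3 and 48 per arm. The within-half SD of baseline is √(1−0.637) = 0.603 of the overall SD. A one-standard-error imbalance is 0.603 × √(2/48) = 0.123 SD, which moves the estimate by 0.123 × 0.3 × 10.01 ≈ 0.37 points. Its square is 0.137. The variance of the estimate without the score is 10.01² × (1 − 0.637 × 0.09) × 2/48 ≈ 3.94, and 0.137/3.94 ≈ 3.5%. That is the figure in Step 3, so it must not be added to it.

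**Step 5: simulation.** Week 52 ANCOVA with 194 evaluable patients, 4,000 replicates per r, a median split and no missing data. For a true effect of −4.06, both models averaged between −4.04 and −4.07. Ratios of empirical standard errors were 1.005, 1.018, 1.027 and 1.052 for r = 0.2 to 0.5. Within a single trial the two models' estimates for a subgroup differed with an SD of 0.28 points (r = 0.2) to 0.62 points (r = 0.5).

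**The case against.** The case for leaving the text alone has substance.

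- **Size.** At r = 0.2 to 0.3 the standard error changes by only 0.8% to 1.8%, and nothing in the SAP supports a correlation as high as 0.5. The calculation also ignores the three randomization strata that stay in this model. If they correlate with baseline, the gain is smaller still. This stands.
- **Status.** The exception is explicit and prespecified. The default model applies only unless otherwise specified, so the text does not contradict itself. The rows are descriptive and no decision depends on them. This also stands.
- **Fitting a cut with its parent score has a cost.** Least-squares means are usually evaluated at one common baseline value. Any single value lies outside the range of one subgroup; a >35 mean could be evaluated at 34, a score none of those patients has. This stands for within-arm means. It does not touch treatment differences, because the model has no treatment-by-baseline term.

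A reader might infer more than the document supports. Lost precision and exposure to chance imbalance might be read as two harms, but Step 4 shows they are one, already reflected in the wider confidence interval. The subgroup estimates might be thought biased, but under randomization they are not. The rest of the forest plot might be taken to share one model, but the GBA, PD-medication and MoCA rows depart from the default too; what sets this row apart is only the missing continuous baseline. Finally, the exception might be read as a mistaken extension of the stratum rule, but the SAP states no reason, so its motive is unknown. The H&Y case in section 2.4.4.2 shows only that overlap between a baseline value and its own cut is not treated consistently as grounds for dropping the value.

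**Conclusion.** The point holds as a modest improvement to a descriptive analysis and does not amount to an error in the plan. Omitting the continuous score makes the two subgroup standard errors about 0.8% to 5.9% larger for r = 0.2 to 0.5 at a 50/50 split, or 1.1% to 8.2% at 20/80. These ranges rest on a normal baseline and on values of r and the split that the SAP does not give. The statement that the estimates are unbiased rests on randomization; the simulation behind it had no missing data. The primary test, the testing hierarchy and the type I error are unaffected.

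**What to change.** In SAP section 2.4.4.1, Subgroup analyses, delete the fourth exception. Keep continuous baseline MDS-UPDRS Part II+III and its time-point interaction in this model, alongside the ≤35/>35 factor and its interactions. Add a sentence saying that within-arm least-squares means for this analysis are evaluated at each subgroup's own mean baseline, so that neither is extrapolated.

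The cost is one deleted line, one added sentence and one model statement with subgroup-specific evaluation points. The covariate is already in the primary model. If the sponsor prefers the exception, the SAP should give the reason and the forest-plot row should carry a footnote. Either way, settle it before treatment is unblinded, since the two models can give visibly different subgroup estimates.

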2.4.4.2 Analyses of secondary efficacy endpoints

Part 1: Dose escalation phase

Not Applicable.

Part 2: Treatment phase

Secondary efficacy endpoints include:

- Change in PD-CRS (total score) from baseline to Week 52.
- Change in MDS-UPDRS Parts I+II+III from baseline to Week 52.
- Change in H&Y stage from baseline to Week 52.

Secondary endpoints will be analyzed using the same MMRM model as for the primary efficacy endpoint. For patients who prematurely discontinued study treatment, data collected more than 7 days after the last IMP administration will be excluded from the analysis of secondary endpoints.

Subgroup analyses

The MMRM model described as primary analysis will be repeated in each of the following subgroups as appropriate, the p-values will not be adjusted for multiplicity and will be provided for descriptive purpose only, and forest plots will be provided:

- GBA mutations (severe vs. non severe) : Severe GBA mutation subgroup will be defined using actual subgroup (not randomization stratum as per IVRS);
- Prior PD medications (yes vs. no): Prior PD medication subgroup will be defined using actual subgroup (not randomization stratum as per IVRS);
- Time since diagnosis (≤ 6 years vs > 6 years);
- Hoehn and Yahr at baseline (< 2 vs. ≥ 2);
- MoCA score at baseline (< 26 vs. ≥ 26): MoCA score subgroup will be defined using actual subgroup (not randomization stratum as per IVRS);

Unless otherwise specified (see below), for each subgroup analysis, the MMRM model will include the fixed categorical effects of treatment group, randomization strata as per IVRS, subgroup factor, time point, treatment-by-time point interaction, strata-by-time point interaction, subgroup factor-by-time point interaction, treatment-by-subgroup factor interaction, and treatment-by-subgroup-by-time point interaction, as well as the continuous fixed covariates of baseline value and baseline value-by-time point interaction. Exceptions will be made for the following subgroup analyses:

- For subgroup analyses by GBA mutation, the MMRM will not include the randomization stratum of severe GBA mutation (yes/no)
- For subgroup analyses by prior PD medication, the MMRM will not include the randomization stratum of use of levodopa/PD medication (yes/no)
- For subgroup analysis by MoCA score at baseline, the MMRM will not include the randomization stratum of MoCA score < 26 (yes/no)

Further subgroup analyses may be performed if deemed necessary for interpretation of results.

Secondary analysis

A secondary analysis will describe the percentage of patients with MDS-UPDRS Part I+II+III score improvement, no change or worsening at Week 52 based on minimal clinically important difference threshold values in patients with Hoehn&Yahr 1&2 (5):

- Improvement will be defined as a change in MDS-UPDRS Part I+II+III ≤ -5.9
- Worsening will be defined as a change in MDS-UPDRS Part I+II+III ≥ 3.7
- No change will be defined as a change in MDS-UPDRS Part I+II+III > -5.9 and < 3.7

Patients without any available assessment at Week 52 will be considered as worsened.

2.4.4.3 Analyses of exploratory efficacy endpoints

Part 1: Dose escalation phase

Descriptive statistics for values and changes from baseline will be presented by treatment arm for each time point. All measurements will be assigned to analysis windows defined in [Section 2.5.4](#), [Table 3](#) in order to provide an assessment for Week 2 to Week 52 time points. For patients who prematurely discontinued study treatment, data collected more than 7 days after the last IMP administration will be excluded from the analysis of exploratory endpoints.

Continuous data will be summarized using the number of available data, mean, standard deviation (SD), median, Q1, Q3 minimum and maximum for each treatment arm at each time point. Categorical and ordinal data will be summarized using the number and percentage of patients in each treatment arm at each time point.

Summary statistics will be provided for the following endpoints:

- MDS-UPDRS: Part II+III score, Part I+II+III score, as well as each part separately (Part I, Part II, Part III and Part IV)
- Hoehn & Yahr scale, as a categorical variable:
 - Stage 0: No symptoms
 - Stage 1: Symptoms on one side of the body only
 - Stage 2: Symptoms on both sides of the body. No impairment of balance
 - Stage 3: Balance impairment. Mild to moderate disease. Physically independent
 - Stage 4: Severe disability, but still able to walk or stand unassisted
 - Stage 5: Wheelchair-bound or bedridden unless assisted
- PD-CRS: Total score, as well as sub-scores: PD-CRS Fronto-subcortical score PD-CRS Posterior-cortical score
- MoCA: Total score, as a quantitative and categorical variable:
 - <26
 - ≥26
- Oral SDMT score
- Trail Making Test: TMT-A, TMT-B and difference between TMT-B score minus TMT-A
- Clinical global impression scale: severity of illness and efficacy index (as a categorical variable)
- Patient Global Impression of Change (as a categorical variable)

Part 2: Treatment phase

All analyses of exploratory efficacy endpoints will be done on Part 2 of the study and will not include patients from Part 1 who are rerandomized in Part 2. Descriptive statistics for values and

changes from baseline will be presented by treatment arm for each time point, p-values for exploratory endpoints may be provided for descriptive purpose only. All measurements will be assigned to analysis windows defined in [Section 2.5.4](#), [Table 6](#) in order to provide an assessment from baseline to Week 156 time points.

Continuous endpoints

Percent change from baseline to Week 52 in DaTSCAN assessment scores (SBR) will be analyzed using an ANCOVA. The model will include the fixed categorical effects of treatment group (GZ/SAR402671 versus placebo), randomization strata (use of levodopa/PD medication: yes/no, MoCA score <26: yes/no and severe GBA mutation: yes/no), as well as the continuous fixed covariate of baseline.

For all other continuous exploratory endpoints, descriptive statistics by visit will be provided for each treatment arm. Summary statistics (including number of available data, mean, SD, median, Q1, Q3, minimum and maximum) will be presented for value, change from baseline and percent change from baseline (when applicable). Further analyses using MMRM (if repeated assessments) or ANCOVA (if single assessment) may be performed when appropriate.

Categorical endpoints

Categorical exploratory endpoints described in [Section 2.1.3.3](#) will be summarized by visit, using the number and percentage of patients in each treatment arm.

Time-to-event endpoints

Time to first occurrence of event of interest data will be presented in terms of cumulative incidence probabilities of occurrence with 95% CI as well as the number of patients at risk, number of patients censored and number of events at key time points (week 13, week 26, week 39 and week 52) using the Kaplan-Meier method and estimates. For time to event exploratory outcomes, statistical comparisons between treatment arms will be carried out using a log-rank test and presented for exploratory purpose only. In addition, Kaplan-Meier curves and summary statistics and estimates showing number of patients at risk and cumulative incidence of events of interest at key time points (week 13, week 26, week 39 and week 52), and appropriate CI may be provided for each treatment arm.

- Time to first initiation of levodopa or other PD medication (for patients not on levodopa/other PD medication at baseline) or to increased dose of levodopa/other PD medication (for patients on levodopa/other PD medication at baseline) is defined as: the time from the date of randomization to the date of first initiation of levodopa or other PD medication (for patients not on levodopa/other PD medication at baseline) or as the time from date of randomization to the date of first documentation of (intensification dose of levodopa/other PD medication (for patients on levodopa/other PD medication at baseline). If no initiation or intensification of levodopa or other PD medication is documented before the first step final analysis date (when all patients from Part 2 have been randomized and have all their data up to Week 52 collected and validated) or database lock, time to first initiation will be censored at the date of last visit or at the date of randomization + 365

days whichever comes first. Definitions of initiation and intensification of PD medication are detailed in Section 2.1.3.3.

- Time to first reduction or stop of levodopa/PD medication (for patients on levodopa/other PD medication at baseline) defined as: the time from the date of randomization to the date of first documentation of reduction or to the date of stop of levodopa/PD medication (for patients on levodopa/other PD medication at baseline). If no reduction or stop of levodopa or other PD medication is documented before the first step final analysis date (when all patients from Part 2 have been randomized and have all their data up to Week 52 collected and validated) or database lock, time to first reduction will be censored at the date of last visit or at the date of randomization + 365 days whichever comes first. Definitions of reduction and stop of PD medication are detailed in Section 2.1.3.3.

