No additional dose escalation of GZ/SAR402671 will occur above the highest proposed dose of 15 mg. All patients must complete the first 4 week course of therapy with subsequent blinded data review by an internal review committee whose purpose is to review blinded data (such as safety, tolerability, and/or relevant clinical endpoints), demonstrating safety/tolerability before dose escalation to the next higher level can occur. Patients will continue to be dosed daily and will be followed every 4 weeks until the completion of Part 1, allowing for additional safety and other exploratory endpoints to be collected. Each cohort will have a 4:1 randomization ratio, and the total sample size will be approximately 15 patients (including 12 on GZ/SAR402671 and 3 on placebo). In Japan, each cohort will have a 3:1 ratio, and the total sample size will be approximately 12 Japanese patients (including 9 on GZ/SAR402671 and 3 on placebo). Therefore, the total sample size in Part 1 will be approximately 27 patients.

At the end of 4 weeks of treatment during the dose escalation part, patients in each cohort will have a lumbar puncture (LP); CSF exposure of GZ/SAR402671 will be measured at 2 time points in Part 1: at pretreatment and Week 4. If there is no CSF exposure at the highest dose level, the study will be stopped.

In Part 2, the GZ/SAR402671 dose will be the highest dose determined to be safe and well tolerated in Part 1. Moreover, CSF exposure must be known. If there is no CSF exposure of GZ/SAR402671, then that dose will not be used in Part 2.

If patients from Part 1 continue to meet eligibility requirements, and are willing to continue in the study, they may enroll in Part 2, but re-randomization will be required; furthermore, they will have to sign another informed consent form. All screening assessments will need to be repeated, except for the genetic screening, magnetic resonance imaging (MRI), LP, and ioflupane I-123 injection DaTSCAN (DaTSCAN), to confirm eligibility of patients from Part 1 to enroll in Part 2.

In Part 2, eligible patients will be stratified based on use of levodopa/PD medication (yes/no), cognitive function (Montreal Cognitive Assessment [MoCA] score <26 [yes/no]) and severe GBA mutation (yes/no). Patients will be randomized in a 1:1 ratio to receive GZ/SAR402671 or placebo for 52 weeks.

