2.1.3.3 Exploratory efficacy endpoint(s)

Part 1: Dose escalation phase

The following endpoints will be analyzed for Part 1:

- Change in Montreal cognitive assessment (MoCA) score, from baseline to 8 weeks
- Change in oral Symbol Digit Modalities Test (SDMT) score, from baseline to 8 weeks
- Change in Trail Making Tests Part A (TMT-A), Trail Making Tests Part B (TMT-B) and difference between TMT-B minus TMT-A score, from baseline to 8 weeks
- Clinical global impression (CGI) scale, including illness severity (CGIS), global improvement of change (CGIC), and therapeutic response at 8 weeks
- Patient global impression of change (PGIC) at 8 weeks

Part 2: Treatment phase

The following exploratory efficacy endpoints will be analyzed for Part 2:

- Change from baseline to Week 26 in biomarkers GL-1 and lyso-GL-1 levels in plasma (percent and absolute change).
- Change from baseline to Week 52 in DaTSCAN assessment scores (percent and absolute change). The Striatal Binding Ratio (SBR) will be calculated for the following brain regions, using the occipital lobe as the reference region:
 - Caudate nucleus: left medial, right medial, left, right
 - Putamen: left medial, right medial, left anterior, right anterior, left, right
 - Corpus striatum: left, right, total
- Time to initiation of levodopa or other PD therapy (for patients not on levodopa/other PD therapy at baseline) or to increased (intensification) dose of levodopa/other PD therapy (for patients on levodopa/other PD therapy at baseline). Initiation or intensification of PD medication will be defined as any of the two following criteria fulfilled:
 - Increase of the dose of a PD medication by at least 50% compared to the dose received at baseline, with maintenance of an increased dose until the end of the 52-week blinded treatment period
 - Initiation of a PD medication not received at baseline, with maintenance of the new PD medication until the end of the 52-week blinded treatment period.

Any technical details are described in [Section 2.5.2](#)

- Time to Reduction of levodopa/PD medication (for patients on levodopa/other PD medication at baseline). Reduction of PD medication will be defined as any of the two following criteria fulfilled:

- Decrease of the dose of a PD medication by at least 50% compared to the dose received at baseline, with maintenance of a decreased dose until the end of the 52-week blinded treatment period

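### The log-rank test for time to PD-medication initiation or intensification is unstratified, although randomization is stratified by baseline PD-medication use (minor, free improvement)

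*SAP*

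**What the plan says.** **Randomization (SAP 1.1).** "In Part 2, eligible patients will be stratified based on use of levodopa/PD medication (yes/no), cognitive function". Cognition is split at a MoCA score of 26, and a third factor is whether the GBA mutation is severe. Allocation to the two arms is 1:1.

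**Endpoint (SAP 2.4.4.3).** For one group the event time is "Time to first initiation of levodopa or other PD medication (for patients not on levodopa/other PD medication at baseline"; for the group already treated, it is the time to a raised dose. Section 2.1.3.3 sets two criteria, either of which is enough: "Increase of the dose of a PD medication by at least 50% compared to the dose received at baseline", or the start of a PD drug not taken at baseline. Either change must be maintained to the end of the 52-week period. Patients without an event are censored at the last visit or at 365 days after randomization, whichever is first.

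**Test (SAP 2.4.4.3).** "statistical comparisons between treatment arms will be carried out using a log-rank test and presented for exploratory purpose only". Kaplan-Meier estimates are planned by treatment arm only.

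**Other Part 2 comparisons.** All three randomization factors are in the primary MMRM, the slope model and the imputation ANCOVA (2.4.4.1), the DaTSCAN ANCOVA (2.4.4.3), and the plasma and CSF GL-1 models (2.4.6.1). Secondary endpoints use the primary MMRM (2.4.4.2).

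**Status of the p-value.** Sections 2.4.4.3 and 2.4.4.4 make p-values for exploratory endpoints descriptive, outside the testing hierarchy.

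**The concern.** The endpoint pools two groups that reach an event by different routes. A patient off PD medication can have an event only by starting a drug. A patient already on it can also have one through a dose rise of at least half. There is no reason to expect equal hazards.

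If the hazards differ, the unstratified test suffers in two ways. Stratified randomization balances the factor between arms, but the pooled log-rank variance takes no credit for that balance and is too large. In addition, the high-hazard group leaves the risk set early, and pooling unlike hazards dilutes the treatment contrast.

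The primary estimand counts MDS-UPDRS outcomes whether or not PD therapy was started or intensified. This endpoint is therefore where a difference in symptomatic treatment would show, and it helps in reading the primary result. A pooled Kaplan-Meier curve over the two groups is also hard to interpret.

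**Working it through.** **1. The plan's own figure.** The SAP states no events, hazard ratio (HR) or power for this endpoint, so the only figure to reproduce is the Part 2 sample size (section 1.3.2: difference 4.06, SD 10.01, two-sided 0.05, 80% power, 10% loss).

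n per arm = 2 × (1.960 + 0.842)² × 10.01² / 4.06² = 2 × 7.849 × 6.079 = 95.4, so 96. The noncentral t version gives 97. Then 97 / 0.90 = 107.8, so 108 per arm, as stated.

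**2. Inputs to the test comparison.**
- From the SAP: 108 per arm, 1:1, censoring at one year, two-sided 0.05. The 10% allowance is used as exponential loss to follow-up.
- Assumed: exponential event times; PD-medication strata exactly balanced between arms; 50%, 70% or 85% of patients on PD medication at baseline; the one-year placebo event risks shown below; HR 1.0 or 0.55; 6000 runs per case.

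**3. Formulas.** Hazard = −ln(1 − one-year risk). For example, 50/30% gives 0.693 / 0.357, a hazard ratio between strata of 1.9; 80/20% gives 1.609 / 0.223, or 7.2.

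Unstratified: Z = U / √V, with U = Σ(treatment indicator − p) and V = Σp(1 − p) over events, where p is the treated share of everyone at risk. Stratified: U and V are computed within each stratum and summed, Z = ΣU / √ΣV. Reject if |Z| > 1.96.

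**4. Results.** Ranges are over the three shares on PD medication.

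| Placebo risk off/on | Type I error, unstratified | Power at HR 0.55, half on medication: unstratified / stratified | Power loss, percentage points |
|---|---|---|---|
| 30/30% | 4.5–5.3% | 53.5 / 53.6% | about 0 |
| 50/30% | 4.2–4.6% | 65.7 / 67.2% | about 1–2 |
| 50/20% | 4.0–4.6% | 58.2 / 61.6% | 2–4 |
| 60/20% | 2.9–3.9% | 62.8 / 69.2% | 4–7 |
| 80/20% | 1.5–2.7% | 64.7 / 79.9% | 13–19 |

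The stratified test rejects 4.1–5.6% under no effect, which is nominal within simulation noise.

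**5. Check on the mechanism.** At 80/20% with half on medication, the simulated null variance of the unstratified Z is 0.654 instead of 1. Then P(|Z| > 1.96) = 2 × [1 − Φ(1.96 / √0.654)] = 2 × [1 − Φ(2.42)] ≈ 1.5%, which matches the table.

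**6. Second set of assumptions.** With HR 0.6, 35% off medication and 4000 runs, power unstratified / stratified is 55 / 58% at 60/30%, 44 / 56% at 70/20% and 33 / 56% at 80/15%. The last is a loss of 23 points.

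**7. Time to reduction.** This endpoint includes only patients on PD medication at baseline, so there is one stratum. ΣU and ΣV then equal U and V, and stratifying by this factor changes nothing.

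**The case against.** **Nothing is decided on this p-value.** That stands. It is descriptive, outside the hierarchy, and the error is on the conservative side. A reader might infer that a confirmatory error rate is at risk; the SAP gives no support for that. Exploratory status does not explain the missing strata, however, because the exploratory DaTSCAN ANCOVA in the same section includes them.

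**The size is assumed.** That stands too. A reader might take 33% against 56% as the expected loss. It comes from the most extreme contrast tried. With permuted blocks in all eight cells, HR 0.6 and 3000 runs, the gain from stratifying was under 1 point at 30/30% and 40/30% and about 1 to 2 points at 50/30%. Losses above 10 points appear only at 70/20% or more extreme contrasts.

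**There is one event definition, not two.** Partly right. Section 2.1.3.3 applies the same two criteria to everyone. Still, the dose criterion cannot be met by a patient with no baseline drug, so the factor limits which criteria can apply. Whether and how far the hazards differ is not documented.

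**Both log-rank tests are at fault.** A reader might infer this because one sentence covers both endpoints. It does not hold for time to reduction, where the factor is constant. MoCA and GBA severity also vary there, but nothing in the SAP shows that either predicts a reduction of PD medication.

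**Why not all three factors?** Eight cells average 216 / 8 = 27 patients. In the permuted-block runs, eight-cell stratification was generally level with, or about a point below, stratification by PD medication alone.

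**Conclusion.** The point holds for time to initiation or intensification only, as a minor and essentially free improvement. The direction is firm: if the hazard differs by baseline PD medication, the unstratified test is conservative and loses power. The size cannot be derived from the SAP. Over the assumed range it runs from none with equal hazards to about 13–23 percentage points at 80/20% or 80/15%.

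These figures rest on exponential times, a common hazard ratio in both strata and near-exact balance between arms; looser balance would make the unstratified test less conservative. They do not model the requirement that the medication change be maintained. In the cases tried, stratifying by PD medication never cost power beyond simulation noise. The primary and secondary analyses are untouched.

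**What to change.** In section 2.4.4.3, for time to initiation or intensification only, specify a log-rank test stratified by use of levodopa/PD medication (yes/no). State whether the factor is taken from the IVRS record or from baseline data; the primary MMRM uses the IVRS strata. Add Kaplan-Meier estimates by that stratum beside the pooled ones. Leave the test for time to reduction as it is.

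The cost is one sentence in the SAP, one strata term in the program and one extra figure, agreed before unblinding. The factor is already collected, and two strata avoid sparse cells.
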